7.8 Adverse Event Assessment and Recording

All adverse events, exacerbations of concomitant illnesses, or events known to be related to underlying disease processes or concomitant medications are to be recorded on the CRF throughout the study. If a pre-existing condition worsens during the study, the date on which the exacerbation began should be recorded. Onset dates for study treatment-related adverse events must be on or after the date of initial study treatment use.

Adverse event recording will include the date of onset, severity, duration, whether or not the study medication was discontinued because of the event, the treatment given, and the outcome. The Investigator must also assess whether the event was related to the study medication, concurrent drug therapy, underlying disease, a combination of these factors, or if it is unknown. Subjects experiencing an adverse event should be carefully followed to determine outcome.

The Investigator will use the NCI-CTCAE for adverse event monitoring, version 5.0 will be applied in all instances. CTCAE version 4.03 may also be used especially when assessing laboratory tests given the complexity in applying version 5.0 in all instances, see www.lexjansen.com/phuse-us/2020/dh/DH16.pdf

Definitions to grade the severity of the event:

Grade 1: Mild; asymptomatic or mild symptoms; clinical or diagnostic observations only; intervention not indicated.

Grade 2: Moderate; minimal, local, or non-invasive intervention indicated; limiting age-

appropriate ADL.

Grade 3: Severe or medically significant but not immediately life-threatening; hospitalization

or prolongation of hospitalization indicated; disabling; limiting self-care ADL.

Grade 4: Life-threatening consequences; urgent intervention indicated.

Grade 5: Death.

The relationship or association of the study medication in causing or contributing to the adverse event will be characterized as not related, remote, possible, probable, or definite as defined below:

• Not related: Evidence indicates no plausible direct relationship to the study medication

• **Remote:** Suggests other conditions are reasonably likely to account for the event including concurrent illness, progression or expression of the disease state, or reaction to concurrent

medication

• **Possible:** Suggests that the association of the event with the study medication is unknown;

however, the adverse event is not reasonably supported by other conditions

• Probable: Suggests that a reasonable temporal sequence of the event with medication

administration exists and based upon the Investigator's clinical experience, the association

of the event with study medication seems likely

• Definite: Suggests that based upon the Investigator's experience, the association of the

event with the study medication seems very certain.

Planned procedures such as surgery should not be recorded as adverse events. However, the

medical condition for which the procedure was performed should be reported if it meets the

definition of adverse event.

7.9 Reporting Requirements

Any adverse event, defined below, that begins any time between the start of the first dose and

within 28 days after the end of the last dose are to be recorded on the appropriate CRF and in detail

in the source documentation (preferably the electronic medical record directly).

Adverse Event: Any untoward medical occurrence in a subject administered a pharmaceutical

product, which does not necessarily have to have a causal relationship with this treatment. An

adverse event can be any unfavorable sign (including an abnormal laboratory finding), symptom,

or disease temporally associated with the use of the investigational drug, whether or not considered related to the investigational drug.

Serious Adverse Event: An untoward event or reaction that at any dose:

- results in death
- is life-threatening
- results in hospitalization or prolongs existing hospitalization
- results in permanent or significant disability or incapacity
- requires intervention to prevent permanent impairment/damage
- results in congenital anomaly or birth defect

In addition, any important medical event that may not result in death, be life-threatening, or require hospitalization may be considered serious when, based upon appropriate medical judgment, they may jeopardize the patient or subject and may require medical or surgical intervention to prevent one of the outcomes listed in this definition.

Life-threatening: An event which a subject was at risk of death at the time of event. There is a distinction between the severity and the seriousness of an adverse event. Severity is a measurement of intensity, thus a severe reaction is not necessarily a serious adverse event. For example, a headache may be severe in intensity, but would not be serious unless it met one of the criteria for serious adverse events listed previously.

7.10 Serious Adverse Events

Adverse events (AEs) and serious adverse events (SAEs) will be collected from the time the first dose of IP is administered until 28 days after the last dose of IP. Medical occurrences that began prior to the start of study treatment, but after obtaining informed consent will be captured as Medical History/Current Medical Conditions on the CRF. The Investigator or site staff will be responsible for the identification and documentation of events meeting the criteria and definition of an adverse event or serious adverse event, as provided in the study protocol. SAEs assessed as related to study participation (e.g., dosing, protocol mandated procedures, invasive tests, or change in existing therapy) or related to a concomitant medication will also be captured once the subject has taken the first dose of study medication.

In the event of an AE or SAE, it will be the responsibility of the Investigator to review all documentation (e.g., hospital progress notes, laboratory, and diagnostics reports) relative to the event and attempt to establish a diagnosis of the event based on signs, symptoms, and other clinical information. Once the Investigator becomes aware that an SAE has occurred, they are to report the information to MedStar Health within 24 hours and provide an assessment of causality.

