3.2 Primary Endpoint

Incidence of Adverse Events and Serious Adverse Events assessed out to day 60.

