5 STUDY DESIGN

5.1 Study Description

This is a phase 2 proof of concept randomized, double-blind, placebo-controlled trial with the purpose of assessing the safety, tolerability and treatment effect of the orally administered Caspase-1 inhibitor, belnacasan, for the treatment of patients with mild to moderate COVID-19. 20 subjects will be given 900 mg TID of belnacasan and 20 subjects will be given a placebo TID for 28 days, and assessments of safety, tolerability, and treatment effect will be performed for up to 60 days.

At the screening / baseline / day 1 Visit, subjects will provide informed consent and be screened for eligibility based on the Inclusion / Exclusion criteria identified in Section 5.3. Subjects will also receive the first dose of study drug at this visit once study eligibility has been confirmed, and the second dose of study drug will be taken approximately 8-12 hours after the first dose. Study drug will be continued three times daily (morning, mid-day, and nighttime doses) through day 28. Some patients identified will require a PCR-confirmed COVID test, having only had a rapid antigen test. Patients requiring a PCR test can either have one collected with screening labs prior to leaving the MedStar enrollment site or have these labs collected via a home-health research visit at no cost to the potential participant. Prior to study-specific procedures the study team will obtain their consent in-person or by remote consent process. An e-consent platform, Interlace, may also be used to document consent electronically. Once their COVID-19 status is confirmed via PCR they will complete the remainder of their screening/enrollment visit at either MedStar Washington Hospital Center or MedStar Franklin Square within the next 1 to 3 days. The remote consent

process and e-consent will follow MedStar institutional policies and procedures (MG.O-004.06 and MG.O-004.07).

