8.4 Safety & Tolerability Analyses

All safety & tolerability analyses will be performed on the Safety Population. The safety data will be presented in individual listings and summary tables.

Overall safety will be assessed by the number of belnacasan VX-765/RVT-201/MSR-001 dosed subjects experiencing a grade 4 or 5 SAE during the trial. Of 20 subjects enrolled in the belnacasan group, 3 or more developing a grade 4 or 5 SAE probably related to belnacasan would be

considered unlikely due to chance. Therefore, belnacasan will be determined safe if no more than

2 subjects develop a grade 4 or 5 SAE in the belnacasan group probably related to belnacasan.

In terms of stopping rules, should two or more subjects develop a similar Grade 3 SAE that is at

least possibly related to belnacasan or should one or more subjects develop a \geq Grade 4 SAE that

is at least possibly related to belnacasan, the trial will be paused for DSMB safety review.

Primary Endpoint Analysis

Primary endpoints of adverse and serious adverse events (AE/SAE) will be assessed by Poisson

regression for count data. Events will be counted out to 60 days from randomization to belnacasan

or placebo groups. Because some subjects may be followed for less than 60 days, subject follow-

up time will be included in the Poisson regression as the exposure time variable. If counts are not

Poisson-distributed, either over- or under-dispersed, negative binomial regression will be to

analyze AE/SAE events with appropriate adjustment for over/under dispersion. Comparison of

belnacasan vs. placebo will be expressed as the incidence rate ratio (IRR).

Adverse Events

AEs will be coded according to the latest version of the Medical Dictionary for Regulatory

Activities (MedDRA). The intensity/severity of AEs will be graded according to NCI-CTCAE (see

Section 7.3).

TEAEs, AEs leading to study treatment discontinuation, AEs leading to dose interruption, AEs

related to study medication, SAEs, and AEs leading to death will be summarized by system organ

class, preferred term, and study period. A summary of AEs that are CTCAE Grade 3 or higher, as

well as the most frequent preferred terms, will be provided.

If a subject experiences the same adverse events multiple times within a period, then the event will

be counted only once within the period and by greatest severity.

Descriptive statistics will be used to summarize the safety data.

Clinical Laboratory Values

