8.6 Handling of Missing Data

Although every effort will be made to obtain complete data, missing values will likely occur when

data are collected longitudinally. Patterns of missingness over time as well missingness with

MOD00008997 IRB Approved 12/23/2021 - 11/9/2022

Version 2.2 12/14/21 Page 51 of 66

respect to demographic and clinical variables will be assessed. For Poisson and Cox regression analyses, all data can be used up to subject dropout time.

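### AE/SAE recording stops 28 days after the last dose (day 56 at the latest), but the primary endpoint counts events to day 60, and the Poisson exposure is tied to neither window

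*Combined protocol and SAP*

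**What the plan says.** Two sections tie recording to the last dose. Section 7.10 states that AEs and SAEs "will be collected from the time the first dose of IP is administered until 28 days after the last dose of IP". Section 7.9 is worded by onset: events beginning between the first dose and "within 28 days after the end of the last dose are to be recorded on the appropriate CRF". Section 1.3 caps treatment at 28 days.

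The rest of the protocol runs to day 60:

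- Section 3.2, primary endpoint: "Incidence of Adverse Events and Serious Adverse Events assessed out to day 60".
- Section 8.4, primary analysis: "Events will be counted out to 60 days from randomization to belnacasan" or placebo.
- Section 5.1: "assessments of safety, tolerability, and treatment effect will be performed for up to 60 days", with telephone contacts on days 42 and 60. The AE row of Table 1 (Section 5.2) is marked at both.
- Sections 5.3 and 8.1: monitoring and safety data collection continue to day 60 after study drug is stopped, while consent is maintained.
- Section 7.8: all AEs, exacerbations and events linked to "underlying disease processes or concomitant medications are to be recorded on the CRF throughout the study".

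On exposure, Section 8.4 says that subject follow-"up time will be included in the Poisson regression as the exposure time variable". Section 8.6 adds: "For Poisson and Cox regression analyses, all data can be used up to subject dropout time". Neither mentions the period in which AEs are recorded.

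Two provisions limit the damage. Section 7.10 also captures SAEs judged related to study participation, dosing included, with no stated end. Section 3.4, item 3a, collects emergency visits, COVID-19 hospitalizations and deaths to day 60.

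**The concern.** The instructions that govern what goes on the CRF close before the window over which the primary endpoint is defined. Staff who follow 7.9 and 7.10 record over a shortened window for every subject, and the expected AE/SAE count is lower than the endpoint calls for. The shortfall grows with early stopping. If some staff follow 7.8 and Table 1 instead, ascertainment differs between subjects.

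The exposure is a second, linked problem. A subject who stops drug but stays in the study is followed to day 60 while recording may have ended weeks earlier. If early stopping differs by arm, numerator and denominator then drift apart differently in the two arms. Section 5.3 expects stopping mainly through consent withdrawal or intolerance, and allows for stopping when symptoms resolve early. Subjects who withdraw consent are outside the day-60 rule, so the point concerns those who stop drug and stay consented.

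**Working it through.** **Window.** Last recordable onset = min(60, last dose day + 28), counting day 1 as the first dosing day. Counting randomization as day 0 moves each end one day earlier and leaves the conflict unchanged.

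| Last dose | Recording ends | Days of 60 outside |
|---|---|---|
| Day 28 | Day 56 | 4 (6.7%) |
| Day 21 | Day 49 | 11 (18%) |
| Day 14 | Day 42 | 18 (30%) |
| Day 7 | Day 35 | 25 (42%) |

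The day 60 call covers onsets on days 43 to 60 (18 days). For a completer, 14 of those days are in the window and 4 are out. For a last dose on or before day 14, none is in the window.

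**Loss per arm of 20** (20 × 60 = 1,200 person-days). The documents give no stopping rates, so these are assumed.

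- All complete dosing: 20 × 4 = 80 (6.7%).
- Two stop on day 7: 18 × 4 + 2 × 25 = 122 (10.2%).
- Six stop on day 7: 14 × 4 + 6 × 25 = 206 (17.2%).

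**Share of AEs unrecorded.** Let H(t) be the share of 60-day AEs with onset by day t. Under a constant hazard H(t) = t/60. Under a hazard halving every 14 days (assumed), H(t) = (1 − e^(−kt))/(1 − e^(−60k)) with k = ln 2/14, so H(56) = 0.988 and H(35) = 0.868. With a fraction f stopping on day 7, the unrecorded share is 1 − [(1 − f)H(56) + f·H(35)]. For f = 0, 0.1 and 0.3 this is 6.7%, 10.2% and 17.2% (constant) or 1.2%, 2.4% and 4.8% (declining).

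**Rate ratio, true value 1.0.** Arm rate = [(1 − f)H(56) + f·H(s + 28)]/T, where s is the stopping day. The exposure T is either 60 days for all or matched to recording, T = (1 − f)·56 + f·(s + 28).

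| Stopping, belnacasan v placebo | Constant, T = 60 | Constant, matched | Declining, T = 60 | Declining, matched |
|---|---|---|---|---|
| 20% v 20% | 1.000 | 1.000 | 1.000 | 1.000 |
| 30% v 10%, day 7 | 0.922 | 1.000 | 0.975 | 1.058 |
| 30% v 10%, day 14 | 0.949 | 1.000 | 0.987 | 1.040 |
| 20% v 10%, day 7 | 0.961 | 1.000 | 0.988 | 1.028 |
| 10% v 30%, day 7 | 1.085 | 1.000 | 1.025 | 0.945 |

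For example, 30% v 10% on day 7 gives mean recorded time 0.7 × 56 + 0.3 × 35 = 49.7 days against 0.9 × 56 + 0.1 × 35 = 53.9 days, and 49.7/53.9 = 0.922.

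**Against the trial's precision.** The only power figure is in Section 8.7: 80% power at 5% alpha for a difference in rate ratios of over 60%. No base rate is given, so it cannot be reproduced uniquely. A two-sided Wald test on the log rate ratio with 20 per arm reaches 80% power at about 1.64 events per placebo subject for a ratio of 0.4, or about 2.89 for 1.6. Reading the figure as a ratio of 0.4 or 1.6 (assumption), SE(log IRR) = |ln 0.4|/2.802 = 0.327 or ln 1.6/2.802 = 0.168. Then |ln 0.922| = 0.081 is 0.25 or 0.48 SE, and ln 1.058 = 0.056 is 0.17 or 0.33 SE.

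**The case against.** Most of the protocol already points to day 60, and the day 42 and day 60 AE calls are scheduled. Section 7.9 requires events in its window to be recorded but does not forbid later ones, so beside 7.8 it can be read as a minimum. Follow-up time in 8.4 can naturally be read as AE follow-up time, and with matched exposure and a constant hazard the ratio is exactly 1.000. Completers lose only four days. The ratios above need assumed unequal stopping, and 0.92 and 1.06 come from different combinations of hazard and exposure that cannot occur together. The trial also calls itself hypothesis generating and says that it is probably underpowered.

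Much of this stands as a limit on size. It does not remove the conflict, because 7.10 sets an end point and cannot be read as a minimum. If sites are meant to follow Table 1, then 7.9 and 7.10 are wrong as written.

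One further objection is fair: the 1.06 comes from fitting a constant rate to a declining hazard with unequal follow-up, and the fix does not remove that for real dropouts. With recording to day 60 and matched exposure, 30% v 10% withdrawing consent on day 7 gives (0.7 + 0.3 × 0.309)/44.1 against (0.9 + 0.1 × 0.309)/54.7, a ratio of 1.056. The fix restores 1.000 for subjects who stop drug but are followed to day 60, not for those who leave.

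**Conclusion.** The concern holds. Taken literally, Sections 7.9 and 7.10 cannot supply the primary endpoint defined in 3.2 and analysed in 8.4. The day counts follow from the documents alone: at least 4 of 60 days fall outside recording, and 25 of 60 after a last dose on day 7. What is mainly lost is late non-serious AEs and SAEs not assessed as related. The pause rule (7.15) and the criterion for declaring the drug safe (8.4) use related SAEs and are largely unaffected.

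The effect on the rate ratio is conditional and modest. It is nil with equal stopping. Where stopping differs it can go either way, and it stays below half a standard error in the 30% v 10% examples under the assumed reading of 8.7. The case for correction is that the primary endpoint's recording rule and its definition disagree, not that a large bias is expected.

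**What to change.** In Sections 7.9 and 7.10, set the AE/SAE window to run *from the first dose of IP through day 60 post randomization for every dosed subject who maintains consent, whether or not IP has been stopped*. Keep the sentence in 7.10 on related SAEs. In Section 8.4, state that the Poisson exposure covers the same window and ends at the earliest of day 60, withdrawal of consent, loss to follow-up or death.

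Make both changes together. Matching the exposure to the present 28-day window without extending it still gives 1.06 in the declining-hazard example.

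The cost is protocol wording and a few more AE records for subjects who stop drug early. No new contact is needed.

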7.11 Notification of Serious Adverse Events

The Sponsor will report all serious adverse events to regulatory agencies as required. In addition to the serious adverse events described in Section 7.10, other events that in the Investigator's opinion suggest a significant hazard, contraindication, or precaution should be considered serious. This includes, but is not limited to, blood dyscrasias, endocrine disturbances, hemorrhage from any site, or severe skin disorder. Additional examples are intensive treatment for allergic bronchospasm, blood dyscrasias or convulsions.

Subjects who experience an SAE must be given appropriate examinations and treatment. The Investigator must provide written information to the Sponsor as soon as possible.

7.12 Reporting a Serious Adverse Event

All appropriate SAEs will be reported immediately to the FDA per reporting criteria for an IND Safety Report. The event(s) will also be reported locally to the IRB of record when the event meeting reporting criteria per MedStar Health Research Institute IRB policy.

7.13 Departure from Protocol for Emergency or Adverse Event

In medical emergencies, the Investigator should use medical judgment and remove the subject from immediate hazard. As soon as possible after removing the subject from hazard, the Investigator must contact MedStar Health by telephone to permit a decision as to whether the subject may continue in the study. The IRB should also be notified as to the type of emergency and the course of action. The CRF for the subject must capture the departure from the protocol and state the reason.

7.14 Safety Monitoring

A Data Safety and Monitoring Board (DSMB) will be established to monitor the safety of the subjects during the study. The DSMB includes members who are independent of this study and its Sponsor Team, and with relevant clinical expertise, including a good understanding of the safety

of medications for respiratory illnesses. These members may include one or more of the followinga statistician, an infectious disease specialist and/or a pulmonologist. The methodology and the operating procedures for the safety reviews will be developed by the infectious disease specialist and/or pulmonologist in collaboration with the Investigator and will be documented in the DSMB Charter. They will review all SAEs and determine whether the study can proceed or whether protocol modifications are required. The Charter will be submitted to the IND before the trial would commence.

7.15 Stopping Rules

Should two or more subjects develop a similar Grade 3 SAE that is at least possibly related to belnacasan or should one or more subjects develop a ≥ Grade 4 SAE that is at least possibly related to belnacasan, the trial will be paused for DSMB safety review.

7.16 Follow-Up and Final Reports

The Investigator shall provide MedStar Health with an accurate final report within 1 month after completion, termination or discontinuation of the study. The final report may not precede completion of monitoring relevant CRFs.

7.17 Regulatory Aspects

Neither the Investigator nor MedStar Health shall modify this protocol without first obtaining concurrence of the other in writing. All modifications must be submitted to the IRB with approval prior to implementation. Protocol modifications which impact subject safety or the validity of the study must be approved by the IRB and submitted to the FDA before implementation. In the case of a medical emergency to increase safety of subjects, a change may occur immediately, and the IRB and FDA will be notified as soon as possible.

8 DATA MANAGEMENT AND STATISTICS

8.1 Populations for Analyses

The following populations will be considered for statistical analyses.

• Safety & Tolerability Population: All enrolled subjects who have received at least 1 dose of IP (belnacasan or placebo) will be studied. Even if subjects have discontinued study treatment, as long as they maintain consent, they will continue to be in the study and

included in analysis, i.e., their safety and tolerability information will continue to be collected for at least 60 days.

• *Treatment Effect Evaluable Populations*: All enrolled subjects who have received at least 1 dose of IP (belnacasan or placebo) will be studied. Even if subjects have discontinued study treatment, as long as they maintain consent, they will continue to be in the study and included in analysis, i.e., their outcome information will continue to be collected for at least 60 days.

